APPENDIX B: SAFETY TERMS AND ADMINISTRATIVE INFORMATION

1. SAFETY ASSESSMENT AND REPORTING

1.1 Safety reporting

The investigator or site staff is/are responsible for the detection, documentation and reporting of events meeting the criteria and definition of an AE or SAE as provided in this protocol. Each subject will be instructed to contact the investigator immediately should the subject manifest any signs or symptoms they perceive as serious.

Reporting procedures for serious AEs

In order to comply with current regulations on serious adverse event reporting to regulatory authorities, the event will be documented accurately and notification deadlines respected. SAEs will be reported to a safety group (specified members of the study team) and medical monitor immediately (within 24 hours) of the investigators being aware of their occurrence. This safety group includes the Principal Investigator, who acts on behalf of the sponsor for notification of SAEs. SAEs will also be reported to ethics committees, the regulatory authority, and – in subjects who have received vaccine – to the manufacturer of the adjuvant (Novavax) in accordance with reporting requirements and according to required timelines in safety data exchange agreement(s).

1.2 Safety definitions

1.2.1 Definition of an adverse event

An AE is any untoward medical occurrence in a clinical investigation subject, temporally associated with the use of a medicinal product, whether or not considered related to the medicinal product. An AE can therefore be any unfavourable and unintended sign (including an abnormal laboratory finding), symptom, or disease (new or exacerbated) temporally associated with the use of a medicinal product. For marketed medicinal products, this also includes failure to produce expected benefits (i.e. lack of efficacy), abuse or misuse.

Examples of an AE include:

- Significant or unexpected worsening or exacerbation of the condition/indication under study.
- Exacerbation of a chronic or intermittent pre-existing condition including either an increase in frequency and/or intensity of the condition.
- New conditions detected or diagnosed after investigational vaccines administration even though they may have been present prior to the start of the study.
- Signs, symptoms, or the clinical sequelae of a suspected interaction.
- Signs, symptoms, or the clinical sequelae of a suspected overdose of either investigational vaccines/ antimalarial medications or a concurrent medication (overdose per se should not be reported as an AE/SAE).
- Signs, symptoms temporally associated with vaccines/antimalarial drug administration.

Research Proposal Submission Form for a study involving human subject enrollment WITH specimen collection

Document No.: FTM ECF-033-01

Page 39 of 52

- Pre- or post-treatment events that occur as a result of protocol-mandated procedures (i.e. invasive procedures, modification of subject's previous therapeutic regimen).

Examples of an AE DO NOT include:

- Medical or surgical procedures (e.g. endoscopy, appendectomy); the condition that leads to the procedure is an AE/SAE.
- Situations where an untoward medical occurrence did not occur (e.g. social and/or convenience admission to a hospital, admission for routine examination).
- Anticipated day-to-day fluctuations of pre-existing disease(s) or condition(s) present or detected at the start of the study that do not worsen.
- Pre-existing conditions or signs and/or symptoms present in a subject prior to the first study vaccination. These events will be recorded in the medical history section of the CRF.

1.2.2 Definition of a serious adverse event

A SAE is any untoward medical occurrence that:

- Results in death,
- Is life-threatening,

Note: The term 'life-threatening' in the definition of 'serious' refers to an event in which the subject was at risk of death at the time of the event. It does not refer to an event, which hypothetically might have caused death, had it been more severe.

- Requires hospitalization or prolongation of existing hospitalization,

Note: In general, hospitalization signifies that the subject has been admitted at the hospital or emergency ward for observation and/or treatment that would not have been appropriate in the physician's office or in an out-patient setting. Complications that occur during hospitalization are also considered AEs. If a complication prolongs hospitalization or fulfils any other serious criteria, the event will also be considered serious. When in doubt as to whether 'hospitalization' occurred or was necessary, the AE should be considered serious.

- Hospitalization for elective treatment of a pre-existing condition (known or diagnosed prior to informed consent signature) that did not worsen from baseline is NOT considered an AE.

- Results in disability/incapacity

Note: The term disability means a substantial disruption of a person's ability to conduct normal life functions. This definition is not intended to include experiences of relatively minor medical significance such as uncomplicated headache, nausea, vomiting, diarrhoea, influenza like illness, and accidental trauma (e.g. sprained ankle) which may interfere or prevent everyday life functions but do not constitute a substantial disruption.

- Is a congenital anomaly/birth defect in the offspring of a study subject.

Research Proposal Submission Form for a study involving human subject enrollment WITH specimen collection

Document No.: FTM ECF-033-01

Page 40 of 52

- Spontaneous pregnancy loss

Medical or scientific judgment should be exercised in deciding whether reporting is appropriate in other situations, such as important medical events that may not be immediately life-threatening or result in death or hospitalization but may jeopardize the subject or may require medical or surgical intervention to prevent one of the other outcomes listed in the above definition. These should also be considered serious. Examples of such events are invasive or malignant cancers, intensive treatment in an emergency room or at home for allergic bronchospasm, blood dyscrasias or convulsions that do not result in hospitalization.

1.2.3 Solicited adverse events

Occurrence of solicited AE from the date of each vaccination to 7 days of each vaccination will be recorded.

Solicited local (injection-site) adverse events - The following local (injection-site) AEs will be solicited:

All age groups
Pain at injection site
Redness at injection site
Swelling at injection site
Bruising at injection site

Systemic solicited adverse events - The following general AEs will be solicited:

Adult
Fatigue
Fever
Diarrhoea
Nausea
Vomiting
Headache
Myalgia
Arthralgia
Chills

Note: Temperature will be recorded in the evening. Should additional temperature measurements be performed at other times of day, the highest temperature will be recorded in the CRF.

1.3 Clinical laboratory parameters and other abnormal assessments qualifying as adverse events or serious adverse events

In absence of diagnosis, abnormal laboratory findings (e.g. clinical chemistry, haematology, and urinalysis) or other abnormal assessments that are judged by the investigator to be clinically significant will be recorded as AE or SAE, if they meet the definition of an AE or SAE. Clinically

Research Proposal Submission Form for a study involving human subject enrollment WITH specimen collection

Document No.: FTM ECF-033-01

Page 41 of 52

significant abnormal laboratory findings or other abnormal assessments that are present at baseline and significantly worsen following the start of the study will also be reported as AEs or SAEs. The investigator will exercise his or her medical and scientific judgment in deciding whether an abnormal laboratory finding or other abnormal assessment is clinically significant.

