This study is a randomized, open-label, single centre, Phase 2 trial of R21/Matrix-M™ in healthy Thai adults. A total of 120 participants will be enrolled and randomized into one of three study arms in a ratio of 5:5:2 as described in Section 6.4.4. Each arm will have 50 participants (for arm 1 and 2) and 20 participants (for arm 3).

- For arm 1 and 3, the eligible volunteers will be asked to come into the Hospital for Tropical Diseases to receive the study agents as out-patient on Day 0 (the day of vaccination), Day 1, Day 2, and Day 7 of Study Months 0, 1 and 2; and on Day 0 of Study Months 3 and 6. There are a total of 15 study visits.
- For arm 2, the eligible volunteers will be asked to come into the hospital to receive the study agent (vaccination only) as out-patient on the day of vaccination (Day 0) and Day 7 of Study Months 0, 1 and 2; and on Day 0 of Study Months 3 and 6. There are a total of 9 study visits.

**Research Proposal Submission Form
for a study involving human subject enrollment WITH
specimen collection**

Document No.: FTM ECF-033-01

Page 16 of 52

Table 2. Vaccine and drug administration

Timepoints	Month Day of month	Scr.	Study period														
			M0				M1				M2						
			0	1	2	7	0	1	2	7	0	1	2	7			
Interventions	Vaccination (Group 1 and Group 2)		x					x						x			
	DHA/piperaquine (Group 1 and Group 3)		x	x	x			x	x	x				x	x	x	
	PQ (single low dose primaquine) (Group 1 and Group 3)		x					x						x			

B6.2 Investigational Products:

1) R21/Matrix-M™

Description of Vaccine: The candidate R21 vaccine to be used has been developed by Jenner Institute and manufactured under cGMP conditions at Serum Institute India Private Limited (SIIPL). R21 is produced to high levels in *Hansenula polymorpha* yeast in fermenters. The purified R21 antigen (drug substance) is released after testing, by SIIPL QC Department using qualified and validated methods. The quality released drug substance is used, for manufacturing drug product after appropriately diluting to 20 µg/mL using formulation buffer. The formulated blend is fill finished in siliconized glass vials (4 mL capacity) at a targeted concentration of not less than 20 µg/mL. Each vial is filled with 0.65 mL of the drug product to enable withdrawal of 0.5 mL. The final formulation has 20 mM Tris, 15% sucrose, 30 mM magnesium chloride, pH 7.4.

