Informed Consent		x																		
Eligibility screen		x																		
Inclusion / Exclusion criteria		x	x				x				x									
Enrolment			x																	
Allocation			x																	
Interventions	Vaccination (Group 1 and Group 2)		x				x				x									
	DHA/piperazine (Group 1 and Group 3)		x	x	x		x	x	x		x	x	x							
	PQ (single low dose primaquine) (Group 1 and Group 3)		x				x				x									
Assessments	History of fever, current axillary temperature*	x	x	x	x	x	x	x	x	x	x	x	x	x	x	x				
	Full medical history, vital signs, physical examination	x	x				x				x									
	Ask about any concomitant medication	x	x	x	x	x	x	x	x	x	x	x	x	x	x	x				
	Assessment of any adverse event(s)		x	x	x	x	x	x	x	x	x	x	x	x	x	x				
	Assess for any withdrawal criteria		x	x	x	x	x	x	x	x	x	x	x	x	x	x				
	Blood tests						Unit (mL)													
	P. falciparum test**						0.5				0.5					0.5				
	CBC	2	2			2				2				2						
	Biochemistry ALT, AST, CREA, BUN, Bilirubin	3	3			3				3				3	3					
	HBsAg, HCV, HIV	1																		
	Immunology panel ^b		20				20				20				20	20				
	Piperazine levels***		1	1	1	1	1	1	1	1	1	1	1	1						
	Blood volume per visit (mL)	6	26	1	1	6	21.5	1	1	6	21.5	1	1	6	25	20.5				
	Maximum cumulative blood volume (mL)															144.5				
Electrocardiogram (ECG)		x																		

**Research Proposal Submission Form
for a study involving human subject enrollment WITH
specimen collection**

Document No.: FTM ECF-033-01

Page 21 of 52

Urine pregnancy test	x	x				x				x					
Diary card provided		x				x				x					
Diary card return						x				x					x

* Axillary temperature will be recorded from D0-D7 visits after each vaccination. If the symptoms are indicated to COVID-19, COVID-19 test will be done. If COVID-19 positive is indicated, then hospital guideline for COVID-19 case management will be followed. Study team will make decision whether or not to withdraw volunteer from the study case by case.

** *P. falciparum* test for purposes of indicating whether volunteer has been exposed, and not as an assessment of protection.

*** Piperaquine levels for group 1 and 3 only. Additional drug level assessment for Primaquine will be done, if additional data are required. Blood sample will be collected before each dose (at each visit) and then at day 7 for drug levels assessment.

- a. first day of M6
- b. the immunology panel consists of assays to be processed at UK laboratories and may include:

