Document No.: FTM ECF-033-01

Page 23 of 52

be prepared by MORU statistician based on random numbers generated in STATA. The randomization sealed envelopes will be prepared by Clinical Trials Support Group (CTSG).

B6.4.4 Randomisation

Randomization numbers will be generated in blocks, for the 3 study arms in a ratio of 5:5:2, as follows:

- R21/Matrix-M™ + DHA-PIP+PQ (Arm 1)
- R21/Matrix-M™ alone (Arm 2)
- DHA-PIP+PQ alone (Arm 3)

Study participants will be assigned the next available randomization number on the list, and thus will be randomly allocated to Group 1, 2, or 3. This is an open-label study. Participants and clinical investigators will not be blinded to group allocation.

B6.4.5 First vaccination or anti-malarial medications initiation (Month 0 / Day 0 visit)

Participants in Group 1 and 2 will be vaccinated by intramuscular (IM) needle injection into the deltoid region of the arm. Participants in Group 1 will also receive anti-malarial medications. Participants in group 3 will receive anti-malarial medications only.

The study participants will be observed closely for at least 30 minutes following the administration of each study vaccine, with appropriate medical treatment readily available in case of an anaphylactic reaction.

An axillary thermometer, tape measure and a paper diary card for solicited AEs will be given to each participant along with the emergency 24-hour telephone number to contact the on-call study physician if needed. Diary cards will collect information on the timing and severity of the following solicited AEs (Table 8):

Table 8. Solicited AEs

Local solicited AEs	Systemic solicited AEs
Pain at injection site	Fever
Redness at injection site	Diarrhoea
Swelling at injection site	Nausea
Bruising at injection site	Vomiting
	Fatigue
	Headache
	Muscle pain (Myalgia)
	Joint pain (Arthralgia)
	Chills

Participants will be instructed on how to self-assess the severity of these AEs. There will also be space on the diary card to self-document unsolicited AEs, and whether medication was taken to relieve the symptoms.

**Research Proposal Submission Form
for a study involving human subject enrollment WITH
specimen collection**

Document No.: FTM ECF-033-01

Page 24 of 52

***B6.4.6 Subsequent vaccination (or subsequence rounds of anti-malarial medications) visits
(Month 1 / Day 0 and Month 2 / Day 0 visits)***

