5. STATISTICAL ANALYSES OF PRIMARY SAFETY ENDPOINTS

Safety analysis will be performed on patients allocated to receive vaccination. The percentage of subjects with at least one local AEs with at least one general AE (solicited and unsolicited) and with any AE during the 7-day or total follow-up period up to 28 days after the last vaccine dose and overall will be tabulated with exact 95% CI. The percentage of doses followed by at least one local AE (solicited and unsolicited), by at least one general AE (solicited and unsolicited) and by any AE during the 7-day or the total follow up period up to 28 days after the last vaccine will be tabulated with exact 95% CI. The same computations will be done for Grade 3 AEs, for any AEs considered related to vaccination and for any Grade 3 AEs considered related to vaccination. The percentage of subjects reporting each individual solicited local AE (any grade and Grade 3) and solicited general AE (any grade, Grade 3, any related, Grade 3 related, resulting in medically attended visit) during the 7-day follow-up period (Day 0-6) after each vaccine dose and overall will be tabulated for each group. Similarly, the percentage of doses followed by each individual solicited local and general AE will be tabulated, overall vaccination course, with exact 95% CI. For fever, the number and percentage of subjects reporting fever by half degree (°C) cumulative increments during the first seven days (Day 0-6) after each vaccine dose and overall will be tabulated. Similar tabulations will be performed for any fever with a causal relationship to vaccination and Grade 3 ($> 39.5^{\circ}\text{C}$) causally related fever. The percentage of subjects reporting unsolicited AEs from the date of the first vaccine dose up to 28 days after the last vaccine dose will be tabulated by group and by MedDRA preferred term with exact 95% CI. Similar tabulation will be done for Grade 3 unsolicited AEs, for any causally related unsolicited AEs and for Grade 3 causally related unsolicited AEs. The percentage of subjects reporting SAEs and pregnancies will be described in detail. The percentage of vaccinated subjects reporting AEs of specific interest (meningitis and pIMDs) will be described in detail.

Thus, in summary, the safety analysis will be as follows:

- Frequency (%) of occurrence of solicited local and general AEs within seven days (day of vaccination and six subsequent days) after each vaccination with exact 95% CI by group and severity.

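### Fever is recorded as the day's highest reading, and Arm 1 has clinic readings on Days 1 and 2 that Arm 2 lacks, so as written the descriptive Arm 1 v Arm 2 fever contrast is not like for like; the size is unknown.

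*Protocol*

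**What the plan says.** Protocol Appendix B 1.2.3 sets the routine measure: "Temperature will be recorded in the evening". It then provides for other readings on the same day: "Should additional temperature measurements be performed at other times of day, the highest temperature will be recorded in the CRF".

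The evening reading is available in every arm, because Protocol B6.4.5 states: "An axillary thermometer, tape measure and a paper diary card for solicited AEs will be given to each participant".

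Table 5 also has a clinic row, "History of fever, current axillary temperature", marked at every visit column including Days 1 and 2 of Months 0, 1 and 2. Its footnote reads: "Axillary temperature will be recorded from D0-D7 visits after each vaccination".

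The visits differ by arm (Protocol B6.1 and Table 6). Arms 1 and 3 attend "as out-patient on Day 0 (the day of vaccination), Day 1, Day 2, and Day 7 of Study Months 0, 1 and 2". For Arm 2 the entry is "vaccination only) as out-patient on the day of vaccination (Day 0) and Day 7 of Study Months 0, 1 and 2".

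Fever is defined as 37.5 °C or above by the axillary route (Appendix B 1.5.1). SAP 5, like Protocol Appendix B 1.6.1, tabulates "the number and percentage of subjects reporting fever by half degree (°C) cumulative increments during the first seven days (Day 0-6) after each vaccine dose". Neither document limits solicited fever to the evening value, gives Arm 2 matching readings, or adjusts for the difference.

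**The concern.** The highest of several readings cannot be lower than any one of them, so the recorded value depends on how many readings are taken. Here that number differs by arm by design, on two days inside the fever window.

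The primary objective is vaccine safety with and without concurrent antimalarials. Arm 1 v Arm 2 is the contrast that isolates adding the drugs to the vaccine. Fever is a solicited event, and solicited events are a primary endpoint in Protocol B6.3.1. A short fever on the morning of Day 1 or 2 can be counted in Arm 1 and missed in Arm 2. The antimalarials could then appear to add to the vaccine's reactogenicity when part of the difference comes from the visit schedule. With 50 participants per arm, one participant is 2 percentage points.

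**Working it through.** **1. Visit totals.** Protocol B6.1 states 15 visits for Arms 1 and 3 and 9 for Arm 2.
- Arms 1 and 3: 1 screening + 3 rounds × 4 (Days 0, 1, 2, 7) + Month 3 + Month 6 = 15.
- Arm 2: 1 + 3 × 2 (Days 0, 7) + 2 = 9.

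Both figures are reproduced. The difference of 6 is exactly Days 1 and 2 of three rounds.

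**2. Scheduled readings in Day 0-6.** Day 0 clinic readings are common to all arms and left out. Day 7 visits are also common to all arms.
- Arm 2: 7 evening readings × 3 rounds = 21.
- Arms 1 and 3: (7 + 2) × 3 = 27, or 27/21 = 1.29 times as many.

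**3. Excess in the tabulated rate, simple model.** Let b be the share of participants with fever over the course on evening readings. Let q be the chance that one Day 1 or Day 2 clinic reading is 37.5 °C or above in a participant with no evening fever. Both are assumptions. The rate in Arm 1 is then 1 − (1 − b)(1 − q)^6, with no true difference between arms.

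| b | q | Arm 1 rate | Excess (points) |
|---|---|---|---|
| 10% | 0.2% | 11.1% | 1.1 |
| 10% | 1% | 15.3% | 5.3 |
| 10% | 2% | 20.3% | 10.3 |
| 20% | 0.2% | 21.0% | 1.0 |
| 20% | 2% | 29.1% | 9.1 |

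The upper end reflects the assumed ceiling of 2% for q, not a limit in the documents. At q = 5% and b = 10% the formula gives 33.8%.

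**4. Excess with correlated readings, by simulation.** 400,000 participants per scenario. Assumptions: mean axillary temperature 36.4 °C; SD 0.2 °C between participants, 0.15 °C between days, and 0.15 or 0.3 °C within a day; post-dose rise drawn from a half-normal with scale 0.4, 0.7 or 1.0 °C, in full on Days 0 and 1 and halved on Day 2.
- Daytime readings as high as evening ones: excess 1.5 to 5.3 points.
- Daytime 0.2 °C lower: 0.2 to 1.8 points.
- Daytime 0.4 °C lower: 0 to 0.5 points.

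**5. Illustration for a single episode.** Assumptions: evening reading at 20:00, clinic reading at 10:00 on Days 1 and 2 only, onset uniform over the 48 hours of Days 1 and 2, no extra home readings. Counting hours from the start of Day 1, Arm 2 is read at hours 20 and 44, and Arm 1 also at hours 10 and 34. The next reading in either arm is at hour 68. An episode of d hours is caught if a reading falls within it.

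| d (hours) | Arm 2 | Arm 1 | Arm 1 catches missed in Arm 2 |
|---|---|---|---|
| 6 | 12/48 = 25% | 24/48 = 50% | 50% |
| 12 | 24/48 = 50% | 42/48 = 87.5% | 43% |
| 18 | 36/48 = 75% | 44/48 = 91.7% | 18% |
| 24 | 100% | 100% | 0% |

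**The case against.** **Merging is not explicit.** The note in Appendix B 1.2.3 concerns solicited events, which are collected by diary and home thermometer. The clinic temperature is a separate row of Table 5, follow-up visit data have their own CRF pages (Protocol B6.4.7), and a table of participants reporting fever fits diary data. A reader might take it as settled that clinic values overwrite diary values and that the fever rate is biased upward. The documents do not say so. What remains is that the note's wording covers readings at other times of day and nothing excludes clinic ones. If they were meant to be excluded, that sentence is missing.

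**Scope.** A reader might infer a problem in both drug arms. Arm 1 v Arm 3 is unaffected because their visits are identical. Arm 3's place in the fever table is itself unclear: SAP 5 limits safety analysis to participants allocated to vaccine, while its Table 4 has a no-vaccine column.

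**No test.** A reader might infer an inflated false-positive rate. Safety is reported as percentages with exact 95% confidence intervals by group, so only a descriptive contrast is affected. This objection stands.

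**Size.** The catch percentages describe single episodes starting on Days 1 and 2, whereas the endpoint is any fever over Day 0-6, so they are not the bias in the tabulated rate. Treating the 10:00 reading as continuing every day would raise the Arm 1 figures to 92% at 12 hours and 100% at 18 hours, but the extra visits stop after Day 2. A feverish Arm 2 participant with a thermometer may well take extra readings, which narrows the gap.

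**Remedy.** Keeping the highest reading is a sensitive safety rule, and replacing it outright would lose genuine daytime fevers. That is a good reason to retain it and add a second row.

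**Conclusion.** The concern holds as differential ascertainment of unknown size. On the natural reading of Appendix B 1.2.3 with Table 5, Arm 1 has six more scheduled chances per course to be recorded as febrile than Arm 2. Any error from those readings raises Arm 1. The excess is about 0 to 10 percentage points under the assumptions above (b of 10% or 20%, q of 0.2% to 2%, or the simulated readings). It is close to zero if daytime temperatures run about 0.4 °C below evening ones, and it shrinks if Arm 2 participants take additional home readings. The documents support no narrower figure. They also do not support a statement that the observed fever rate will be biased by a given amount. The point deserves correction because it bears on the primary safety objective and costs little to settle.

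**What to change.** Keep the highest-reading rule for safety reporting and leave clinical care unchanged. In the CRF, record whether each temperature is the evening diary value or another reading. In SAP 5, add solicited fever (any, half-degree steps, Grade 3) by arm from the evening diary reading only, and state that the Arm 1 v Arm 2 fever contrast is read from that row. Every arm then has 7 scheduled readings per dose and 21 per course in that row, so the excess due to scheduled clinic readings is zero by construction.

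The cost is one CRF field and one extra table row with its SAP sentence. The fever rate in the added row will be somewhat lower, because fevers seen only in the daytime are not counted there; they remain in the highest-reading row.
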